#### *Post-Traumatic Stress Disorder Checklist (PCL)*

The PCL (Blevins, Weathers, Davis, Witte, & Domino, 2015) is a validated 17-item, self-report measure of PTSD symptoms based on DSM criteria. Items are rated from 0 to 4 (0 = not at all, 4 = extremely). Total scores range from 17-85. Higher scores indicate higher post-traumatic stress symptoms. This measure was only collected at baseline.

#### *Insomnia Severity Index (ISI)*

The ISI (Bastien, Vallières, & Morin, 2001; Morin, Belleville, Bélanger, & Ivers, 2011) is a 5-item measure of the respondent's perceptions of their insomnia, such as severity of sleep-onset and sleep maintenance difficulties. Items are rated from 0 to 4 (0 = not at all, 4 = very much). Total scores range from 0 to 28. Totals are categorized as follows: no clinically significant insomnia (0-7), subthreshold insomnia (8-14), clinical insomnia (moderately severe) (15-21), clinical insomnia (severe) (22-28). The ISI has demonstrated good reliability and validity, particularly in detecting changes in perceived insomnia.

#### *Headache Pain Catastrophizing Scale (HPCS)*

The HPCS (Sullivan, 1995; Wheeler, Williams, & Morley, 2019) is a modified version of the validated Pain Catastrophizing Scale (substitutes "headache" for "pain" in the questions). The HPCS is a 13-item measure used to assess catastrophic thinking related to headache with three subscales: rumination, magnification, and helplessness. Item responses range from 0 to 4 (0 = not at all, 4 = all the time). Total scores range from 0 to 52, with higher scores indicating higher levels of catastrophizing. A total score of 30 or higher indicates clinically significant catastrophizing.

#### *Headache Management Self-Efficacy Scale (HMSE)*

The HMSE (French et al., 2000) is a 25-item measure used to assess a respondent's perception of their ability to take actions to prevent and manage their headaches and headache-related disability. Item responses range from 1 to 7 (1 = strongly disagree, 7 = strongly agree). Total scores range from 25 to 175 with higher scores indicating higher levels of headache management self-efficacy. The HMSE has demonstrated excellent reliability and construct validity.

#### *Veterans RAND-12 Health Status Inventory (VR-12)*

The VR-12 (Selim et al., 2009) is a 12-item measure used to assess health related quality of life and to produce physical and mental health component scores.

#### *Migraine-Specific Quality of Life Questionnaire (MSQ)*

The MSQ (Martin et al., 2000) is a 14-item measure of headache-related quality of life with three dimension scores: role restrictive, role preventive, emotional. It has demonstrated evidence of construct validity and reliability.

### **Data collection plan: retention**

- i. Plans to promote participant retention and complete follow-up, including list of any outcome data to be collected for participants who discontinue or deviate from intervention protocols

Participants will be eligible to receive a total of \$150 in gift cards for completion of all data collection measures.

## Data management

- i. Plans for data entry, coding, security, and storage, including any related processes to promote data quality (eg, double data entry; range checks for data values). Reference to where details of data management procedures can be found, if not in the protocol

Research staff will enter participant assessment data directly into a secure database. In addition, we will use a secure database (QUALTRICS) for participants to enter their self reported outcome data directly into a database.

## Statistics: outcomes

- i. Statistical methods for analysing primary and secondary outcomes. Reference to where other details of the statistical analysis plan can be found, if not in the protocol

Analyses comparing the TENACITY and EHUT control groups on primary and secondary outcomes will be completed using linear mixed models for hierarchical and longitudinal data (patients are nested within site). The mediating and/or moderating effects of patient-level (e.g., age, gender, and depression) and facility-level variables will be examined.

We will conduct an intention-to treat analysis. A generalized mixed effects model will evaluate the primary outcome of number of headache days and fixed effect of study arm, Visit (time) (Month 3 vs Baseline) and their interaction. Days will be clustered within Veteran and a first order autoregressive structure will be used for the relationship between adjacent days.

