## Objectives

The objective of this study is to conduct a pilot randomized controlled trial (RCT) and determine the feasibility of the implementation of a cognitive behavioral therapy (CBT-HA) protocol for headache delivered via telemedicine (TENACITY) compared to enhanced headache usual treatment (EHUT).

The investigators will recruit Veterans diagnosed with chronic migraine during the one-year recruitment period across the 3 VAMCs. The investigators will randomize eligible Veterans to participate either in the TENACITY intervention (n=50) or treatment as usual (n=50).

The specific aims are threefold:

Aim 1: To develop a bundle of evidence-based practice (EBP) implementation strategies to engage 3 VA Medical Centers [2 Headache Centers of Excellence HCoEs and 1 general neurology service] and facilitate their local adaptation and implementation of Cognitive Behavioral Therapy (CBT) (TENACITY) through the vehicle of telehealth services.

Aim 2. To conduct a pilot RCT and determine the preliminary efficacy and feasibility of TENACITY compared to TAU across 3 VA sites. We will conduct a superiority analysis.

Hypothesis 2: Veterans receiving TENACITY will experience a statistically significant reduction in routine clinical headache metrics: headache frequency [headache days per month] (primary outcome), headache-related impairment and psychological symptoms (secondary outcomes) compared to enhanced headache usual treatment at 3 and 6 months.

Aim 3: The investigators will conduct exploratory cost analysis of TENACITY from the Veteran's perspective, using inputs from the pilot RCT, and a two-year budget impact analysis from the VHA's perspective, incorporating the costs of implementation as well as direct costs (and cost-savings,) of providing the TENACITY intervention over all HCoEs to VHA.

Hypothesis 3: TENACITY will be cost-effective and provide value to Veterans and VHA.

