### Interventions: modifications

- i. Criteria for discontinuing or modifying allocated interventions for a given trial participant (eg, drug dose change in response to harms, participant request, or improving / worsening disease)

Treatment length and content is able to be modified and adjusted based on clinician discretion and mutual agreement with the participants.

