### Outcomes

[figure not shown]
The primary outcome to be evaluated is change in the number of self-reported headache days during the past 31 days at 3 months compared to baseline. This outcome is considered the gold standard for prospective migraine research.

Secondary outcomes include the change in headache-related impairment and psychological symptoms at 3 and 6 months compared to baseline. These include a battery of well-validated health questionnaires of functioning and symptoms that are tracked as part of routine headache care services both in VA and non-VA healthcare systems and include the following: Migraine-Specific Quality of Life Questionnaire (MSQ); MIDAS; Headache-specific Pain Catastrophizing Scale (HPCS); Headache Management Self-Efficacy Scale (HMSE); Post Traumatic Stress Disorder (PCI-5); PHQ-9; GAD-7; Veterans RAND VR-12; Insomnia Severity Index (ISI).

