## Primary Outcomes Collection

Reduction of headache days in the 31 days prior to the 3-month post-start of treatment mark is the primary outcome; reduction in headache days in the 30 days prior to the 6-month post-start of treatment mark will allow for measurement of cumulative benefit and persistence of efficacy.

The VA Annie mobile application (Saleem et al., 2020) will be utilized as the platform for a daily headache diary. A protocol has been designed (Table 1) to send daily automated text messages to each participant for a total of 31 consecutive days. Participant responses are stored in the Annie system and are accessible by study staff. If a participant responds that they had a headache, eight additional questions are asked as indicated in Table 1. After being prompted with an Annie question, if the participant does not respond, a reminder message is sent every twenty minutes, with a maximum of three reminders per question.

Q	Text	Response Options	Action
1	Hello, it's Annie. Did you have a headache today?	Yes – HA 2 No – HA 1	If HA 2 → Q2 If HA 1 → Q9
2	On a scale from 0-10, with 0=none and 10=worst, how severe was the headache?	PN 0 – PN 10	If response → Q3
3	Was the pain worse on one side of your head?	Yes – SD 2 No – SD 1	If response → Q4
4	Was the pain pounding/throbbing?	Yes – PD 2 No – PD 1	If response → Q5
5	Did light bother you?	Yes – LT 2 No – LT 1	If response → Q6
6	Did sound bother you?	Yes – SO 2 No – SO 1	If response → Q7
7	Did you feel nauseated or sick to your stomach or vomit?	Yes – VO 2 No – VO 1	If response → Q8
8	Was the pain made worse with routine activities such as walking or climbing stairs?	Yes – MV 2 No – MV 1	If response → Q9
9	On a scale from 0-10, with 0=none and 10=worst, how much did the headache interfere with your life today?	IN 0 – IN 10	

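### The primary model names no term for Veterans changing by different amounts and no standard-error method, so its arm-by-visit interval can be too narrow

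*Combined protocol and SAP*

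**What the plan says.** The Outcomes section defines the primary outcome as "change in the number of self-reported headache days during the past 31 days at 3 months compared to baseline". Under Primary Outcomes Collection, the diary app will "send daily automated text messages to each participant for a total of 31 consecutive days", and the first question each day asks whether there was a headache.

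Statistics: outcomes gives a generalized mixed effects model with "fixed effect of study arm, Visit (time) (Month 3 vs Baseline) and their interaction". It then adds: "Days will be clustered within Veteran and a first order autoregressive structure will be used for the relationship between adjacent days". The model's stated response is the count of headache days. An earlier general sentence covers primary and secondary outcomes with linear mixed models, patients being nested in sites. The section does not state a random visit effect, a Veteran-by-visit effect, a distribution or link, or a standard-error method. The two following sections add only adjustment for sex and imputation.

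The Objectives section plans a superiority analysis, and Hypothesis 2 says that "Veterans receiving TENACITY will experience a statistically significant reduction in routine clinical headache metrics". It gives no alpha or sidedness. The Sample size section sets 50 per arm from staff resources and calls the trial a pilot for preliminary efficacy.

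**The concern.** An autoregressive structure on adjacent days makes sense only for daily records, so the natural fit is a daily model with a Veteran intercept, AR(1) and model-based standard errors. The effect of interest is a difference between arms in change from baseline to month 3. A Veteran intercept takes the same value at both visits and cancels out of that change. AR(1) correlation dies away within days. No stated term is left to carry real differences between Veterans in how much they change, so the 31 days at each visit count as nearly independent information about change.

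If true changes vary, the standard error of the interaction is then too small. The interval is the main efficacy product of a pilot, and this one also plans a significance claim. Too narrow an interval would overstate the preliminary evidence for TENACITY.

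**Working it through.** The plan has no SD, effect size or power figure to reproduce. The check asks how often the test rejects when there is no arm effect.

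**From the documents:** 50 per arm; 31 daily records per visit; baseline and month 3; at least 8 headache days at baseline.

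**Assumed:** two-sided 5%; complete diaries; day-to-day correlation ρ of 0 to 0.4; SD of true change between Veterans, τ, of 0 to 6 days.

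**1. Closed form (rough).** For a Veteran with daily headache probability p, the variance of a 31-day count is s² = 31·p(1−p)·(1+ρ)/(1−ρ). The SD of observed change is √(2s² + τ²), but the natural fit in effect uses √(2s²). The ratio of reported to true standard error is R = √[2s²/(2s² + τ²)], and the false-positive rate is 2[1 − Φ(1.96R)]. The 95% half-width is 1.96 × SD × √(2/50).

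With p = 0.5:
- ρ = 0: s² = 31 × 0.25 = 7.75 and 2s² = 15.5. At τ = 2, R = √(15.5/19.5) = 0.892, giving 8.1%. At τ = 4, R = √(15.5/31.5) = 0.70, giving 16.9%; the half-width is 1.54 days reported against 2.20 true.
- ρ = 0.25: 2s² = 15.5 × 1.25/0.75 = 25.83. At τ = 2 the rate is 6.8%. At τ = 4 it is 12.4%, with half-width 1.99 against 2.54.

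This assumes that the fitted residual absorbs none of τ², so it is only a guide.

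**2. Simulation.** Binary diaries were generated with the baseline threshold enforced (mean about 21.7 days) and ρ of 0, 0.2 or 0.4. There were 5000 replicates per linear scenario and 1000 per logistic scenario. Two-sided false positives, %:

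| True-change SD (days) | 0 | 2 | 4 | 6 |
|---|---|---|---|---|
| Veteran intercept + AR(1), linear | 4.0-4.4 | 6.1-8.5 | 11.5-20.6 | 17.5-30.8 |
| Veteran intercept + AR(1), logistic | 4.8-5.7 | 7.3-9.1 | 11.0-20.3 | 17.7-31.4 |
| AR(1) only, linear | 0.9-1.1 | 2.3-2.7 | 4.9-9.8 | 10.5-20.0 |

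At ρ = 0.2, the intercept + AR(1) linear fit prints a half-width of 1.57 days against a true 1.74 (SD 2), and 1.60 against 2.18 (SD 4).

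The same linear fit reaches a 10% false-positive rate at a true-change SD of 2.3, 2.8 and 3.6 days for ρ = 0, 0.2 and 0.4. These correspond to an observed SD of change in the 31-day count of 3.9, 4.8 and 5.9 days, which the trial's own data can show.

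A second simulation with a different generator agrees in direction and order. It gave 5.7-6.3% with no variation in true change, and 12-38% at observed SDs of change of about 5 to 9 days.

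**3. Candidate remedies, same simulation as step 2.** False positives were 4.4-5.8% (linear) and 4.1-5.9% (logistic) with Veteran-clustered standard errors; 3.4-5.6% and 4.0-5.8% with a Veteran-by-visit effect; and 4.4-5.8% with one count per visit and a free residual variance.

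**4. Does any count model work?** No. A binomial model of the count with only a Veteran intercept has the same likelihood, up to a constant, as the daily logistic model with independent days. In 400 replicates with independent days it gave 4.0, 11.0, 20.0 and 38.8% at SDs of 0, 2, 4 and 6. A Poisson count with only a Veteran intercept erred mostly the other way: 0, 0, 1.5 and 7.3%.

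**The case against.** **The faulted model is partly a reading.** The plan names neither a Veteran intercept nor model-based standard errors, and clustering within Veteran does not exclude a random visit effect or clustered errors. This stands. A reader might infer that the final analysis will be anti-conservative. The documents do not support that; they support only that the stated terms leave it open.

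**The direction depends on the reading.** With residual AR(1) and no intercept, the test is conservative at small SDs (about 1-3% at SD 0-2) and passes 5% only at about 2.8-4.0 days. This stands too.

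**The unit is not fully clear.** The model's response is named as a count, while the next sentence speaks of adjacent days. Daily records are the likelier reading, but a count is possible. A reader might infer that a count removes the problem; step 4 shows that this holds only with a suitable variance term.

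**The size is assumed.** The plan will look for moderators ("The mediating and/or moderating effects of patient-level (e.g., age, gender, and depression) and facility-level variables will be examined") and allows flexible treatment ("Treatment length and content is able to be modified and adjusted based on clinician discretion"). A reader might take this as evidence that true changes vary widely. It shows only that the plan does not assume equal change. Other text points the other way: usual headache care continues, and the comparator therapy differs mainly between sites. Stronger day-to-day correlation also shrinks the effect. At ρ = 0.6 and p(1−p) = 0.16, s² = 31 × 0.16 × 4 = 19.84, which gives about 6% at τ = 2 and 9.8% at τ = 4.

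**It is a pilot.** No confirmatory claim rests on this test, which lowers the stakes. A superiority analysis is nevertheless planned.

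**Conclusion.** The concern holds in conditional form. As written, the primary model names no term for differing change and no standard-error method, and its most natural fit gives too narrow an interval unless true changes hardly vary between Veterans. If they do not vary, that fit shows no material inflation. Confidence is high on the mechanism and medium on the size, because the SD of true change, the day-to-day correlation and the test level are all assumed. The finding is that this model can give a wrong interval, not that the final analysis will. It should be settled before analysis, since defensible readings of one sentence lead to materially different intervals.

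**What to change.** In Statistics: outcomes, state one of these for the primary outcome:

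1. Add a Veteran-by-visit random effect (random visit slope) to the daily model.
2. Keep the daily model and use standard errors clustered by Veteran with a small-sample correction.
3. Analyse one 31-day count per Veteran per visit with a model that has a free residual variance: a linear mixed model, or ANCOVA on the count adjusted for baseline. If a binomial or Poisson model is preferred, add a Veteran-by-visit or overdispersion term, or use Veteran-clustered standard errors.

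In each case, state the two-sided alpha, report the month-3 arm difference in headache days with a 95% CI, and say that this model replaces the general linear mixed model sentence for the primary outcome. If a logistic link is kept, convert to days (31 × averaged predicted probability, with the interval from resampling Veterans).

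The cost is one or two sentences, somewhat more with a logistic link, and no new data. The interval becomes wider but correct: about 2.2 instead of 1.6 days half-width at an assumed true-change SD of 4 and day-to-day correlation of 0.2. If true changes do not vary, option 1 is slightly conservative (3.4-3.7%, linear).

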## Statistics: additional analyses

- i. Methods for any additional analyses (eg, subgroup and adjusted analyses)

We will adjust for participant sex.

## Statistics: analysis population and missing data

- i. Definition of analysis population relating to protocol non-adherence (eg, as randomised analysis), and any statistical methods to handle missing data (eg, multiple imputation)

We will evaluate missing data and will employ imputation for participants who complete at least 28 of 31 days of headache diary for our primary outcome.

## Methods: Monitoring

### Data monitoring: formal committee

- i. Composition of data monitoring committee (DMC); summary of its role and reporting structure; statement of whether it is independent from the sponsor and competing interests; and reference to where further details about its charter can be found, if not in the protocol. Alternatively, an explanation of why a DMC is not needed

We have established a Data Safety Monitoring Committee that is comprised of two clinical psychologists employed by the VHA one of which is also a research scientist and an

epidemiologist employed by VHA. This committee is independent from the sponsor and the research team.

### Data monitoring: interim analysis

- i. Description of any interim analyses and stopping guidelines, including who will have access to these interim results and make the final decision to terminate the trial

No interim analysis will be conducted.

### Harms

- i. Plans for collecting, assessing, reporting, and managing solicited and spontaneously reported adverse events and other unintended effects of trial interventions or trial conduct

Oversight for assessing potential harms or adverse events will be provided by [name] (PI) and co-investigator, [name] MD, a board-certified headache specialist and Director of the West Haven VAMC Headache Center of Excellence, and [name] [name], a site PI and [name], a site PI .

Research staff are trained to report any adverse events promptly to the PI and the project manager. Participants will be encouraged to report any adverse events they have experienced. We anticipate that using this active identification method will allow us to identify all adverse events in a timely manner.

The project manager will be responsible for reviewing the adverse events reports of all participants each day, reporting the information to the PI, and if needed, reporting the adverse event to the IRB. As per VA policy, we will notify the IRB promptly using the appropriate form when a serious, study-related adverse event occurs. If the adverse event is serious, unanticipated or requires revision of the Project Description or Consent Form, we will notify the IRB by telephone as soon as possible and always within 24 hours. A formal report will be provided within 2 business days. All adverse events will be reported yearly to the IRB for review regardless of seriousness or relationship to the research. Because of this policy, the IRB will be providing parallel review of adverse events along with the PI. We believe this will ensure stringent oversight and early identification of any unexpected risks to human subjects.

All adverse events will be monitored by the principal investigators and graded as “expected” or “unexpected” and graded for severity. All unexpected and serious adverse events will be reported to the IRB within 24 hours. Adverse events will be discussed and graded by the entire study team at the weekly team meetings.

All study personnel will have access to community mental health contacts (local phone numbers, 1-800 numbers) and will be trained on emergency plans for subjects found to be actively suicidal. All patients who have scores indicating depression diagnosis and who have not been diagnosed or treated will be advised to contact their primary care provider for evaluation. We will also contact the primary care providers of all undiagnosed/untreated subjects whose scores indicate severe depression and/or suicidality.

## Auditing

- i. Frequency and procedures for auditing trial conduct, if any, and whether the process will be independent from investigators and the sponsor

This study is subject to triennial audits and any additional audits according to the policies of the local IRB at each study site.

## Ethics and dissemination

### Research ethics approval

- i. Plans for seeking research ethics committee / institutional review board (REC / IRB) approval

Approval by local site ethics committees, IRBs, and R&D committees will be obtained prior to any study procedures taking place. Any relevant modifications to the study requiring review by these entities will be submitted and approved before implementing them.

### Protocol amendments

- i. Plans for communicating important protocol modifications (eg, changes to eligibility criteria, outcomes, analyses) to relevant parties (eg, investigators, REC / IRBs, trial participants, trial registries, journals, regulators)

All protocol modifications will be agreed upon by investigators and submitted to the appropriate IRBs for approval. Should the modifications potentially affect a participant's willingness to participate in the study, the modifications will be discussed with participants and an updated informed consent will be signed if applicable.

